6.3.3 SPECIMEN PREPARATION, HANDLING, AND STORAGE

A 2mL skim milk-tryptone-glucose-glycerol (STGG) swab will be used for both molecular and classical bacteriological culture methodologies. A request form with details of the swab will accompany each sample. Once the samples reach the laboratory, details will be entered into the Laboratory Information System for recording, workup and subsequent reporting. The original samples can be stored at -80°C until processed. Once processing is complete, the samples will be retained at -80°C. All specimens will be subjected to DNA extraction using the Roche MagNaPure extraction platform for subsequent molecular testing using routine and standard protocols. The remaining fluid will be restored at -80°C in case of a need for further analysis.

6.3.4 SPECIMEN SHIPMENT

The STGG swabs are the collection swabs and transport material of choice, since they are suitable for both molecular and bacterial culture assays. Once collected, they can be kept cool in styrofoam containers(eskies) and transported to the nearest SA Pathology collection centre or delivered to the Frome Road or nRAH laboratories directly. Transport of swabs from SA Pathology Collection centres to the central laboratory will be kept cool using validated transport methods for biological specimens.

7 ASSESSMENT OF SAFETY

7.1 REPORTING PROCEDURES

7.1.1 ADVERSE EVENT REPORTING

Adverse events and Serious Adverse events are not expected from Study Parts 2 & 3. Although we do not expect any SAE's to occur in relation to this study, any that occur will be immediately reported to the Principal Investigators and to the relevant Human Research Ethics Committee. In particular, if the study related SAE is fatal or life threatening, notification to the Principal Investigator and vaccine manufacturer must be made immediately, irrespective of the extent of available event information. Only SAEs that are assessed as related to study participation will be reported to the REC.

Reporting period

For each participant, the study related serious adverse event reporting period beings at the time of the participant's informed consent, and continues until study participation is complete. If the study investigators become aware of a study related serious adverse event after study completion this will also be reported.

Causality assessment

The investigator is required to assess and record the causal relationship. For all SAEs, sufficient information should be obtained by the investigator to determine the causality of each SAE. The investigator is required to follow-up the SAE until the event and/or its sequelae resolve or stabilize at a level acceptable to the investigator.

An investigator's causality assessment is the determination of whether there exists a reasonable possibility that any study processes caused or contributed to an adverse event.

- Specific Serious Adverse Events (SAE) reporting requirements are not needed in this as this study is non-interventional
- Any SAE assessed as related to study participation will be reported to the REC.
- The investigators will provide or arrange for prompt diagnosis and medical treatment of any research related injury experienced by a study subject. Investigators will also notify the vaccine manufacturer of any research related injuries from Study Parts 2 or 3.

7.2 SAFETY OVERSIGHT

Safety oversight will be under the direction of the PI, as for study 1.

8 CLINICAL MONITORING

As per Phase 1

9 STATISTICAL CONSIDERATIONS

9.1 DESCRIPTION OF STATISTICAL METHODS

9.1.1 GENERAL APPROACH

Logistic regression with adjustment for confouding will be used to identify factors associated with carriage and to compare carriage rates annually and between vaccinated and unvaccinated students. Changes in carriage between baseline and 3 months later will be evaluated using logistic regression with generalised estimating equations. In all analyses of carriage prevalence, effects will be described using odds ratios with 95% confidence intervals.

For comparing the difference in PCR +ve samples after freezing of the sample at 6 hours and 48 hours, we will compare paired proportions using a logistic model with generalised estimating equations, and assess agreement using a Kappa statistic.

9.1.2 BASELINE DESCRIPTIVE STATISTICS

Descriptive statistics will report percentages, means with standard deviations, median, and/or range (as appropriate) for the following:

- Age
- Socio-economic Index for Areas (SEIFA) categories. Calculated from suburb data
- Categorical outcomes for household size
- Categorical outcomes for number people that smoke in each house
- Prevalence of *N. meningitidis* all genogroups carriage
- Prevalence of N. meningitidis serogroup B carriage

9.2 SAMPLE SIZE

Study Part 2:. Assuming a carriage prevalence of approximately 8%, a sample size of 500 university students will allow for estimation of carriage prevalence with a precision of +/- 2.4%, where precision is defined as the half-width of a 95% confidence interval.

Study Part 3:. Assuming the carriage prevalence of disease causing genogroups of *N.meningitidis (A, B, C, W, X, Y)* in school leavers in 2018 is 8%, a sample size of 4,096 students per year will provide 80% power to detect a 20% relative reduction in carriage prevalence between 2018 and 2019 (two tailed alpha = 0.05).

10 QUALITY ASSURANCE AND QUALITY CONTROL

As per Phase 1.

11 ETHICS/PROTECTION OF HUMAN SUBJECTS

11.1 ETHICAL STANDARD

As per Phase 1

11.2 INSTITUTIONAL REVIEW BOARD

As per Phase 1

11.3 INFORMED CONSENT PROCESS

11.3.1 CONSENT/ASSENT AND OTHER INFORMATIONAL DOCUMENTS PROVIDED TO PARTICIPANTS

Consent forms describing study procedures, and risks will be given to the participant and written documentation of informed consent is required prior to commencing any study procedures.

11.3.2 CONSENT PROCEDURES AND DOCUMENTATION

Informed consent is a process that is initiated prior to the individual agreeing to participate in the study and continues throughout the individual's study participation. Consent forms will be HREC approved and the participant will be asked to read and review the document. [name], MO will answer any questions that may arise. All participants will receive a written explanation in terms suited to their comprehension of the purposes, procedures, and potential risks of the study and of their rights as research participants. Participants will have the opportunity to carefully review the written consent form and ask questions by speaking with the study staff. The participant will sign the informed consent document prior to any procedures being done for the study. The participants may withdraw consent at any time throughout the course of the study. The participant will be provided with an copy of the information sheet.

11.4 PARTICIPANT AND DATA CONFIDENTIALITY

Participant confidentiality is strictly held in trust by the participating investigators and SA Pathology. This confidentiality is extended to cover testing of biological samples in addition to the clinical information relating to participants. Therefore, the study protocol, documentation, data, and all other information generated will be held in strict confidence. No information concerning the study or the data will be released to any unauthorised third party without prior written approval of the sponsor.

Study investigators will store identifiable information in locked offices and compactors in the Vaccinology Immunology Research Trials Unit (VIRTU) at the Women's and Children's Hospital. Electronic data including student name, address, and telephone number will be stored on a protected sever at the University of Adelaide.

Study participant research data, which is for purposes of statistical analysis and scientific reporting, will be transmitted to and stored at the Women's and Children's Hospital. This will not include the participant's contact or identifying information. The study data entry and study management systems used by VIRTU research staff will be secured and password protected. At the end of the study, all study databases will be de-identified and archived at the University of Adelaide.

This study is not a human genome-wide association study and no human genetic material will be analysed.

11.4.1 RESEARCH USE OF STORED HUMAN SAMPLES, SPECIMENS OR DATA

• Intended use: samples and data collected under this protocol may be used to investigate *N.meningiditis* carriage, density, serotype, genotype, and antigen type. No genetic testing will be performed on human material.

- Storage: samples and data will be stored using codes assigned by SA Pathology or the study team. Data will be kept in password-protected computers. Only investigators, study staff, and SA Pathology staff will have access to the samples and data. Patient identification data will be entered into the secure laboratory information system. Consolidated reports can then be generated from this system. All staff who have access to the laboratory information system are bound by the Public Sector rules and regulations pertaining to patient and result confidentiality.
- Tracking: Data will be tracked using accredited SA Pathology procedures and systems.
 - Disposition at the completion of the study: All stored samples will remain in frozen storage at SA Pathology and may be used for further testing to assess the N. meningititidis and associated microbiota.

11.5 FUTURE USE OF STORED SPECIMENS

After the study is completed, biological samples will be stored at SA Pathology and/or University of Adelaide. These samples could be used for research into *N.meningiditis* genotype and vaccine antigen coverage. Samples will be provided with a code-link that will allow linking the biological specimens with the phenotypic data from each participant, maintaining the masking of the identity of the participant if they are to be sent to external laboratories.

During the conduct of the study, an individual participant can choose to withdraw consent to have biological specimens stored for future research. However, withdrawal of consent with regard to biosample storage will not be possible after the study is completed.

12 DATA HANDLING AND RECORD KEEPING

12.1 DATA COLLECTION AND MANAGEMENT RESPONSIBILITIES

Data collection is the responsibility of the EN, RN, MO, and trial staff at VIRTU. The investigator is responsible for ensuring the accuracy, completeness, legibility, and timeliness of the data reported.

Clinical laboratory data will be entered into existing SA Pathology data systems. These will then be exported and combined in a database on the University of Adelaide Server (AHTA). The data system includes password protection and internal quality checks, such as automatic range checks, to identify data that appear inconsistent, incomplete, or inaccurate.

Once matched and the data is cleaned it will be de-identified. The Investigator is responsible for keeping a code list so that it is possible to link a participant code to a particular participant. This code list will be kept separately on the University of Adelaide server to ensure that in the case of an emergency, a participant can be identified.

12.2 STUDY RECORDS RETENTION

As per Phase 1

13 STUDY ADMINISTRATION

13.1 STUDY LEADERSHIP

As per Phase 1

1. PREFACE

This Statistical Analysis Plan (SAP) describes the planned analyses and reporting for the South Australian Men B Vaccine Herd Immunity Study, Phase 2, Study Part 3.

The following documents were reviewed in preparation of this SAP:

- B Part of It Study Protocol (Version 5, 7th November 2017)
- B Part of It Student Questionnaire (Version 3, 23 December 2016)
- B Part of It School Leaver Questionnaire (Version 5, 20 November 2017)

2. STUDY METHODS

2.1 Overall study design

Observational cross sectional study of South Australian school leavers in 2018 and 2019.

2.2 Participant inclusion criteria

- South Australians who were in enrolled in year 12 at school in the preceding year of recruitment
- Written consent

3. GENERAL ISSUES FOR STATISTICAL ANALYSIS

3.1 Analysis software

All analyses will be performed using SAS version 9.4 or later, and Stata Release 15 or later.

3.2 Methods for outliers and missing data

Outliers and missing data will be queried during data collection and the statistical analysis. Unless confirmed as a data entry error, outliers will not be excluded from the primary analysis.

Given the cross-sectional nature of the study, only small amounts of missing data (<10%) are anticipated. Analyses will therefore be performed on complete cases only under an assumption that data are missing completely at random. It has been suggested that results of statistical analyses are likely to be biased when the amount of missing data is greater than 10% (Bennett, 2001). Should the amount of missing data in the analysis of the primary objective exceed this proportion, or if the missing completely at random assumption is clearly violated, conclusions instead will be based on analyses using multiple imputation, performed under a missing at random assumption using $m=50$ imputations. In these analyses, missing data will be imputed using chained equations, with univariate linear, logistic and multinomial logistic regression models used to impute incomplete continuous, binary and categorical variables, respectively. All variables included in the intended analysis models will be incorporated into the univariate models. Other auxiliary variables useful for improving the prediction of missing values will be added to the imputation model as appropriate.

3.3 Methods for violations of modelling assumptions

The analyses in Sections 6.5.6 and 6.5.7 are based on an assumption of a linear relationship between the log odds of the outcome and months since vaccination. If there is evidence that these assumptions may be invalid, appropriate techniques to account for non-linearity will be applied.

4. DESCRIPTIVE STATISTICS

4.1 Baseline characteristics

A descriptive comparison of the 2018 and 2019 groups will be conducted on the baseline characteristics presented in the following table.

Baseline characteristic	Categories
Age - years	-

Baseline characteristic	Categories
Sex	Female Male
Participation in the High School B Part of It Meningococcal Study	Yes No Unsure
Meningococcal B vaccine status	Yes (<= 12 months since dose 2) Yes (> 12 months since dose 2) Partial (only one dose) No
Meningococcal ACWY vaccine status	Yes (<= 12 months) Yes (> 12 months) No
Working status	Full time work Part time work Part time work + study Full time student Not working or studying Other
Smoking	Yes No
Cigarettes / day	-
Smoked e-cigarette in the last week	Yes No
Number of times smoked an e-cigarettes in the last week	-
Smoked water pipe in the last week	Yes No
Number of times smoked a water pipe in the last week	-
Number of persons/room	0 to 1

Baseline characteristic	Categories
	>1 to ≤2 >2
Ethnicity	Aboriginal Torres Strait Islander Caucasian Asian Middle East African Pacific Islander Other
Other smokers at home	Yes No
Antibiotics	None Stopped last month Stopped last week Yes, currently taking
Mouth wash used in the last month	Yes No
Times used mouth wash in last month	-
Number of days out in last week	-
Drank alcohol in the last month	Yes No
Number of days drank alcohol in last month	-
In those that drank in the last month, number of drinks on a typical drinking day	-
Days drank in the last month X typical drinking day	-
Number of people kissed in the last week	-
In current relationship	Yes No
Is partner a smoker	Yes

Baseline characteristic	Categories
	No N/A

Means and standard deviations will be reported for continuous variables, while frequencies and percentages will be reported for categorical variables.

4.2 Working status categories

Mutually exclusive working categories grouped as described below:

- Full time work (full time work regardless of other categories)
- Part time work (working part time +/- gap year +/- looking for work)
- Part time work + study (working part time and studying at university of TAFE +/- looking for work)
- Full time study (exclusively TAFE or university student)
- Not working or studying (not working full time, part time, studying)
- Other
- Missing

5. SAMPLE SIZE ESTIMATION

Assuming the carriage prevalence of disease associated genogroups of *N. meningitidis* (A, B, C, W, X, Y) in school leavers in 2018 is 8%, a sample size of 4,096 students per year will provide 80% power to detect a 20% relative reduction in carriage prevalence between 2018 and 2019 (two tailed alpha = 0.05).

6. STATISTICAL METHODS FOR GROUP COMPARISONS

Throughout this section the following details are provided for each outcome variable:

- Outcome: a description of the outcome variable.
- Effect: the measure of effect to be reported.
- Analysis: the type of statistical analysis to be performed.

For each outcome variable, statistical significance will be assessed at the 0.05 level using a two-sided superiority test. In addition to effect estimates and p-values, 95% confidence intervals will be reported to express uncertainty about the estimated effects.

6.1 Vaccination Definition

School leavers who participated in the High School B Part of It RCT will be considered vaccinated if they have received two doses of Bexsero[®] at least one month prior to the date of the throat swab.

Vaccination will be confirmed in students who previously participated in the high school cluster randomised trial through the original study database. Participants who did not take part in the cluster randomised trial will be asked to provide consent to contact their immunisation provider to confirm vaccination history.

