6.2 Adjustment

Adjustment will be made for risk factors that had a two-tailed p-value < 0.05 in the multivariable model for baseline disease-causing carriage in the High School B Part of It RCT (see <https://clinicaltrials.gov/ct2/show/NCT03089086> for description of study). These include current cold or sore throat (no, yes), smoking cigarettes (no, yes), smoking water pipes (no, yes), days out at a pub/club in last week (0, 1 or more), people kissed in last week (0, 1 or more), and ethnicity (Caucasian, Asian, Aboriginal or Torres Strait Islander, Other). Adjustment will also be made for alcohol consumption in the last month (no, yes), as this emerged as an important risk factor

for disease-causing carriage in a preliminary analysis of 2018 School Leaver data. Previous vaccination with MenACWY (no, yes) and participation in the High School B Part of It RCT (no, yes) will also be considered for inclusion in the adjusted model. In order to address each hypothesis, both unadjusted and adjusted analyses will be performed, with primary conclusions to be based on the results of adjusted analyses. No adjustment will be made for risk factors in the analysis of carriage of genogroups A, C, W and X, as only small numbers of cases are expected to be detected.

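### Does the SAP leave open who counts as vaccinated and unvaccinated with 4CMenB in a way that would upset the secondary comparisons?

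*SAP*

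**What the plan says.** SAP 6.1, the titled vaccination definition, reads "School leavers who participated in the High School B Part of It RCT will be considered vaccinated if they have received two doses of" the vaccine under study. It then adds a timing condition: both doses must fall "at least one month prior to the date of the throat swab". Status is confirmed from the trial database for former RCT participants. For the rest, "Participants who did not take part in the cluster randomised trial will be asked to provide consent to contact their immunisation provider". Protocol 6.2.2 has every participant report prior 4CMenB receipt, with year and month, and asks for verification where possible.

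The baseline table in SAP 4.1 has four 4CMenB levels, among them "Yes (<= 12 months since dose 2" and "Partial (only one dose". It has no one-month cut and no unknown level.

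On missing values, SAP 3.2 says "Analyses will therefore be performed on complete cases only under an assumption that data are missing completely at random". It adds that "if the missing completely at random assumption is clearly violated, conclusions instead will be based on analyses using multiple imputation". In SAP 6.2, "participation in the High School B Part of It RCT (no, yes) will also be considered for inclusion in the adjusted model".

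The definition feeds the vaccinated against unvaccinated odds ratios in SAP 6.5.3 to 6.5.5. It also sets who enters the time-since-vaccination analyses in 6.5.6 and 6.5.7.

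**The concern.** Two groups of students seem to have no settled place.

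- **Recently dosed students.** A student swabbed two weeks after dose 2 is a yes in SAP 4.1. Under 6.1 a former RCT participant with those dates is not vaccinated, yet is neither a one-dose student nor a plain no. Because the one-month rule is written for RCT participants only, a non-RCT student with the same dates could land in the other group. Such students are foreseeable: Protocol 5.3 reminds Group B students of their due doses and of the extra swab in the same message.
- **Students with unconfirmed status.** RCT participants are checked against a database, others only with consent. Unconfirmed status therefore depends on RCT participation, which sits badly with missing completely at random. An analyst might count these students as unvaccinated, drop them or impute them.

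At stake are the size and purity of the reference group in 6.5.3 to 6.5.5. The Protocol rationale (2.2) wants this contrast to help inform vaccine funding.

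**Working it through.** **Sections side by side.** SAP 4.1 describes the 2018 and 2019 samples. SAP 6.1 lies inside section 6, which holds the group comparisons, and nothing in 6.5.3 to 6.5.5 points back to 4.1. A descriptive label without a lower time limit and an analytic definition with one can coexist. SAP 6.5.6 and 6.5.7 count time from the second dose for all vaccinated school leavers, so two doses is the evident meaning for everyone.

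**The plan's own figure.** The per-year size for 8% against 6.4%, two-sided 0.05, 80% power, mean 7.2%:

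n = [1.960·√(2·0.072·0.928) + 0.842·√(0.08·0.92 + 0.064·0.936)]² / 0.016² = 4,096.

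This matches SAP 5 and Protocol 9.2. It concerns the comparison of years, so 4CMenB status does not enter.

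**Base case for the vaccinated contrast (assumed).** The documents do not power this contrast. Inputs:

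- 2 × 4,096 = 8,192 students.
- About two thirds vaccinated (Protocol 2.2): 5,461 against 2,731.
- Carriage of 6.4% and 8%, borrowed from the year comparison.

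OR = (0.064/0.936)/(0.08/0.92) = 0.786. Expected carriers are 349.5 and 218.5, so

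SE(log OR) = √(1/349.5 + 1/5,111.5 + 1/218.5 + 1/2,512.5) = 0.090.

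The 95% interval is about 0.66 to 0.94, and unadjusted power (pooled variance) is 76%.

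**Recently dosed students.** Their number r is not given. Suppose all vaccinated leavers of 2018 are RCT students and half are Group B: 4,096 × 2/3 ÷ 2 = 1,365. If 10% to 30% are swabbed within a month after dose 2, r is 137 to 410. If all are swabbed at or before dose 1, r is 0. The r students are taken from the 5,461. With equal baseline risk, their own carriage runs from 8% (no effect yet) to 6.4% (full effect).

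| r | Counted as vaccinated | Counted as reference |
|---|---|---|
| 55 | 0.786–0.788 | 0.786–0.790 |
| 137 | 0.786–0.792 | 0.786–0.795 |
| 410 | 0.786–0.802 | 0.786–0.809 |

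Example, r = 137 in the reference group at full effect: (2,731 × 0.08 + 137 × 0.064)/2,868 = 0.0792, giving OR 0.795. The shift is ln(0.795/0.786)/0.090, about one eighth of an SE. For r = 410 the largest shift is about a third of an SE, with power 67%. Excluding the 410 leaves the OR at 0.786 and power at 75%.

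**Unconfirmed students, 10% or 30% of the reference group (assumed).**

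- Dropped at random: OR 0.786, power 73% or 66%.
- Counted as unvaccinated when 30% of them were in fact vaccinated: OR 0.791 or 0.802, power 74% or 68%.

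**Time since vaccination (6.5.6).** With flat carriage of 6.4% over months 1 to 24, adding 137 students at month 0 with 8% gives an OR per month of 0.998 instead of 1.000 (SE of log OR 0.008).

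**The case for a change.** The best case for a change is that 6.1 does not define unvaccinated at all, and that harsher inputs give larger movements. Take 410 recently dosed students at half effect. If their baseline risk is 1.3 times that of the others, the OR is 0.816 when they count as vaccinated and 0.768 when they count as reference. At 0.77 times, it is 0.778 and 0.822. Coding alone then moves the estimate by 0.6 to 0.7 of an SE. If 10% or 20% of the truly vaccinated were coded as unvaccinated, the OR would be 0.816 or 0.838 and power 64% or 53%. The 10% switch in SAP 3.2 is tied to the primary objective, so missing vaccination status cannot trip it. SAP 6.2 also mentions a preliminary analysis of 2018 data, so a rule left open could be chosen after data are seen.

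The drafting gap stands, and so does the point about the 10% switch. The sizes carry less weight: neither the counts nor the risk ratios have a source in the documents, and the largest losses require many vaccinated students to be labelled unvaccinated. Nothing in the SAP tells an analyst to do that. The second switch in 3.2, a clear violation of missing completely at random, is not limited by its wording to the primary analysis. The imputation models take in all analysis variables and may add auxiliary ones, so RCT participation can enter. Unconfirmed also need not mean unknown, because the questionnaire records prior receipt and its date. The missing unknown level is no special omission either: sex, smoking and antibiotic use in the same table have none.

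**Conclusion.** No change to the plan is needed. SAP 6.1 is incomplete as drafted, but an analyst can fill the gap from the SAP itself: two doses at least a month before the swab for everyone, and SAP 3.2 for status that remains unknown. Whether one-dose and recently dosed students are set aside or pooled with the reference group is a choice with defensible answers either way. The one modelling step involved, keeping RCT participation in the model, firms up a covariate that SAP 6.2 already considers.

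On the assumed base case (OR 0.786, SE of log OR 0.090), 137 recently dosed students with equal baseline risk shift the OR by no more than 0.009. Larger effects need several hundred such students, unequal risk or systematic miscoding, none of which the documents establish. The contrast was never powered and is exploratory under SAP 6.3. The primary analysis is unaffected.
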